1.0 PROTOCOL TITLE: Evaluation of biomarkers for predicting macronutrient intake

Protocol Version Date: 10/26/2023

Check if this research has U.S. Federal government funding via one or more direct awards or a sub-award. Provide the source of federal support: National Institutes of Health

All other sources of funding:

2.0 PRINCIPAL INVESTIGATOR:

[name], PhD. Professor, Ponder Endowed Chair. Physician Nutrition Specialist. Editor-in-Chief Clinical Nutrition and e-SPEN Journal. Director Center for Translational Research in Aging & Longevity.

3.0 Co- INVESTIGATORS:

[name]. [name] [name] in Biomedical Engineering. Head, Department of Biomedical Engineering. Faculty, Department of Materials Science and Engineering. Center for Remote Health Technologies and Systems.

[name]. Professor, Head Clinical Research. Co-director Center for Translational Research in Aging & Longevity.

4.0 Objectives:

Establish a quantitative relationship between macronutrient intake from fresh meals and the resulting blood and ISF levels of small-molecule metabolites (nutritional biomarkers)

5.0 Background:

Introduction

The increase in plasma concentration of glucose and amino acids (AAs) is directly related to the amount of carbohydrates and protein/free AAs consumed, respectively. However, while glucose dynamics have been studied intensely, the relationship between protein intake and AA levels in ISF is less understood and more complex. Our preliminary results show a different plasma-ISF relationship for individual AAs, with only a few exhibiting strong enough relationships to use ISF levels in predicting plasma levels for liquid meals. It is also unclear whether the ISF concentration is a valid proxy when solid meals are consumed. Therefore, a controlled study with healthy part will be conducted to establish quantitative relationships between compartmental concentrations of macronutrients and metabolites. This study will evaluate the effects of meal composition (macronutrient intake) on the levels of metabolites in blood and interstitial fluid.

Significance

Monitoring and optimizing dietary intake are important for precision nutrition in the treatment of clinical conditions (diabetes, obesity, kidney/liver failure, etc) as well as attenuating loss of muscle function and mass during aging. Processing of macronutrients (carbohydrates, protein, and fat) is believed to be highly personalized. Unfortunately, current methods for personal

IRB NUMBER: IRB2023-0400F
IRB APPROVAL DATE: 4/10/2024

health monitoring only allow accurate measurements of physical activity and do not provide reliable measurement of macronutrient intake or availability of metabolites after digestion. Invasive blood samples are inconvenient and only periodic. While minimally-invasive wearable probes for tracking glucose trends are emerging (e.g., CGMs), no tools currently exist to provide on-demand monitoring of multiple macronutrient metabolites (e.g., glucose + amino acids). Thus, there is a technology gap that could be filled with multi-analyte sensing devices.

Innovation

Interstitial fluid (ISF) levels of metabolites are hypothesized to have complex but consistent relationship with their levels in blood/plasma, such that knowledge of ISF levels may be used to predict both blood levels and macronutrient amounts. An innovative combination of insertable optical reporters combined with wearable readers and advanced computational methods are proposed to provide continuous/on-demand measurement of these metabolites in ISF and used them as “nutritional biomarkers” to predict macronutrient intake

6.0 Inclusion and Exclusion Criteria:

Recruitment & Screening

Healthy older adults (50-75y; equal gender) with a BMI between 25 and 35 will be recruited from an existing database of CTRAL. In addition, we will recruit older adults that respond to distributed flyers and advertisements in the newspaper and to radio announcements in the community of the College Station/Bryan area. Informed consent will be obtained on the screening day before any study related procedures will be performed. If inclusion/exclusion criteria are met, participants are invited to take part in the study.

Inclusion criteria

- Ability to walk, sit down and stand up independently
- Age 50-75 years old
- Ability to lie in supine or slightly elevated position for approximately 13 hours
- BMI between 25 and 35
- Willingness and ability to comply with the protocol

Exclusion Criteria

- Established diagnosis of malignancy
- Established diagnosis of Insulin or non-Insulin Dependent Diabetes Mellitus
- History of untreated metabolic diseases including hepatic or renal disorder
- Currently on anticoagulants (i.e., warfarin, factor X inhibitors or direct thrombin inhibitors)
- History of deep vein thrombosis, pulmonary embolisms, or known clotting disorders
- Presence of acute illness or metabolically unstable chronic illness
- Recent myocardial infarction (less than 1 year)
- Known allergy or intolerance to any of the meal components
- Any other condition according to the PI or nurse that was found during the screening visit, that would interfere with the study or safety of the patient
- Failure to give informed consent or Investigator's uncertainty about the willingness or ability of the participant to comply with the protocol requirements

When during the period from enrollment to completion of the study any condition is developed, whether causing the participant to not meet inclusion criteria or to meet exclusion criteria, they will be excluded from the study.

7.0 Number of Local Participants:

IRB NUMBER: IRB2023-0400F
IRB APPROVAL DATE: 4/10/2024

Up to 40 individuals will be enrolled in the study. For establishing the quantitative relationship between macronutrient food intake and resulting plasma and ISF values of small molecule markers (Aim 1), our initial focus will be on classical time-series techniques, which can operate well with limited training data. Based on a sample size calculation for the machine-learning model to distinguish a 30% difference in protein and CHO amounts with power of 0.8 and significance level of 0.05, we will need 33 healthy participants, 8 meals per participant. Estimating 20% dropout.

8.0 Study-Wide Number of Participants:

n/a

9.0 Study Timelines:

1 screening visit ~2 hours

4 study visits each ~15 hours over the course of 3-6 weeks

Total time: ~62 hours

10.0 Study Endpoints:

Primary Endpoint

- Prediction models of postprandial plasma glucose in relation to the macronutrient content of predefined meals as assessed by plasma and/or ISF concentrations of amino acids, glucose, and/or triglycerides

11.0 Procedures Involved:

The study will take place at the research facility of the Center for Translational Research on Aging and Longevity (CTRAL), Texas A&M University located in the Human Clinical Research Building. The study involves 1 screening visit lasting up to 2 hours and fasting prior to screening is not required. We will screen participants for any disease or condition that could interfere with the studies. We also will perform Dual-energy X-ray absorptiometry (DXA) to measure body composition. We will also ask participants to answer demographic questions, questions about general health and nutrition, eating habits, etc. Demographic characteristics will be collected at baseline. Prior to completion of the study, all participants will also complete a series of questionnaires. Questionnaires are used to assess the current cognitive and mental well-being. Questionnaires, such as the following, may be completed during the study days:

- 3-day food diary to determine habitual dietary intake
- Questionnaire about gut function and symptoms: The Gastrointestinal Symptom Rating Scale (GSRS)
- Questionnaire about activity: Physical Activity Scale for the Elderly (PASE) & Baeck
- Questionnaires about general well-being: Sf36

On each study day, body weight will be measured. Participants will be fed up to 8 different meals (see **Table 1**) with specific nutritional composition (two per day) and then monitored for four hours after the meal. Meals will be spaced at 8 hours to limit overlapping effects. Meal sets will be randomized across study days (see **Table 2**). At the end of the second monitoring period, catheters will be removed and participants will be given an additional meal. Participants will be able to go to the restroom and drink water ad libitum throughout each study day. See **Figure 1** for an overview of the study day. The microdialysis pump which contains the perfuse solution and catheters will be securely affixed to the subjects forearm using coban. See **Figure 2** for a schematic picture of the microdialysis setup and an actual photo of the pump used by CTRAL. This will ensure maintenance of proper placement and collection of samples while out of the

IRB NUMBER: IRB2023-0400F
IRB APPROVAL DATE: 4/10/2024

bed. Participants will return 3 times (4 total study days per participant), where the same procedure will be repeated with meals of different compositions.

Table 1. Type and composition of study meals

Meal Number	Carbohydrate (g)	Protein (g)	Fat (g)	Energy (kcal)
1	40	15	15	355
2	40	15	40	580
3	180	40	15	1015
4	180	40	40	1240
5	180	15	15	915
6	40	40	15	455
7	180	15	40	1140
8	40	40	40	680

All meals will be prepared by a local company ([Heat Ups](#)) to match the composition of the Frozen Meals.

Table 2. Meal sets to be randomized across the study day

	AM Meal	PM Meal	Total Calories (kcal)
Meal set A	Meal 1	Meal 4	1595
Meal set B	Meal 6	Meal 7	1595
Meal set C	Meal 2	Meal 3	1595
Meal set D	Meal 5	Meal 8	1595

Meal sets will be randomized across study days for all participants.

An in-dwelling catheter will be inserted in a peripheral vein of the lower arm or hand to enable blood sampling. The arm will be put in a hot box to allow collecting arterialized venous blood samples. After taking a baseline blood sample (~5 ml), the predefined meal will be consumed within 10 min. Small arterialized venous blood samples (~3 ml) will subsequently be drawn at 30 minutes and then every 60 minutes after for the duration of the study day. This process will be repeated after consumption of Meal 2 on each study visit. Samples will be collected in predefined tubes (15 blood samples, totaling ~60 ml), plasma/serum separated, aliquoted, and stored at -80 Celsius for later assays and/or sent to a local accredited laboratory. A one-time blooddraw (~12 ml) will be collected for measurement of acute clinical chemistry biomarkers.

- Hemoglobin A1C
- Insulin
- Renal function panel (Alb/BUN/Calcium/CO2/Cl/Creat/Glucose/Phosp/Potassium/Sodium)
- Hepatic function panel (ALT, AST, Alb, Alk Phos, Direct bili, Total Bili, Total protein)
- Lipid panel (Total Cholesterol, HDL Cholesterol, LDL Cholesterol, Triglycerides, VLDL Cholesterol)

- CBC (DIFF/PLT) (Hematocrit, Hemoglobin, MCV, MCH, MCHC, RBC, WBC, Platelet count, and percentage and absolute differential counts)
- hsCRP

In the opposite limb, a commercially-available microdialysis catheter will be placed in the forearm following standard operating procedures developed by the European Academy of Allergy & Clinical Immunology Task Force on Skin Microdialysis. Dialysate will be collected in 60-minute aliquots in microvials for the duration of the study day. Microvials will be weighed before and after sample collection. A syringe filled with perfusate containing a mixture of stable tracer-labeled amino acids and glucose will be infused through the syringe pump at a controlled rate (5 μ l/min; total fluid perfused 4.5 ml).

[figure not shown]

Figure 1. Overview Study Day for 91-Micro2

[figure not shown]

Figure 2. Schematic representation (not drawn to scale) and photo of CTRAL's microdialysis pump

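### Section 7.0 states power for a 30% intake difference, but only two widely spaced levels of carbohydrate and protein are fed, so the study cannot show that resolution

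*Protocol*

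**What the plan says.** Section 7.0 of the Protocol gives the only power statement: "Based on a sample size calculation for the machine-learning model to distinguish a 30% difference in protein and CHO amounts with power of 0.8", with significance level 0.05, leading to 33 participants and 8 meals each. The 30% is a difference in the amount eaten, not in the biomarker response. The section does not say from which intake the 30% is measured, or on which scale.

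The meals are in Section 11.0, under "Table 1. Type and composition of study meals". The eight meals are every combination of carbohydrate 40 or 180 g, protein 15 or 40 g and fat 15 or 40 g. Table 2 only pairs them into morning and afternoon sets. The further meal at the end of the day follows catheter removal, so it adds no sampled level.

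Section 4.0 sets the aim: "Establish a quantitative relationship between macronutrient intake from fresh meals" and the resulting blood and interstitial fluid (ISF) levels. On the form of the relationship, Section 5.0 says that the plasma rise "is directly related to the amount of carbohydrates and protein/free AAs consumed", but that "the relationship between protein intake and AA levels in ISF is less understood and more complex". Its Innovation paragraph expects that "knowledge of ISF levels may be used to predict both blood levels and macronutrient amounts". The primary endpoint in Section 10.0 concerns models that relate plasma glucose to the content of the study's own set meals.

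**The concern.** The one property for which the Protocol claims power is the ability to tell apart intakes that differ by 30%. The participants never eat two meals that differ by anything close to that. With two levels per nutrient, the data show the response at the low level and at the high level and nothing between. A statement about a 30% step then rests on the curve assumed to join the two points, and the Protocol states no curve. The Section 5.0 wording on plasma gives a direction, not a functional form.

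Two things are at stake. The power statement describes something that the study cannot demonstrate at any sample size. It also leaves readers free to take a clean separation of 40 from 180 g of carbohydrate, or of 15 from 40 g of protein, as evidence that the 30% target was met.

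**Working it through.** **The stated figure.** Inputs from Section 7.0: n = 33, difference 30%, power 0.80, alpha 0.05. No standard deviation, prediction error or within-person correlation is given, so 33 cannot be recomputed. It can only be inverted. Assuming a two-sided paired comparison with the 30% on the same scale as the SD of the paired difference, n = (SD × (1.960 + 0.842) / 0.30)², so SD = 0.30 × √33 / 2.802 = 0.615. With assumed SDs of 0.5, 0.6 and 0.7 the formula gives n = 22, 32 and 43. So 33 is attainable under an SD that the Protocol does not state; it is neither confirmed nor refuted.

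**Contrasts fed (Table 1).**

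| Nutrient | Low | High | Ratio | From low | From high | 30% step from low | 30% step from high | Gap fed |
|---|---|---|---|---|---|---|---|---|
| Carbohydrate | 40 g | 180 g | 4.5 | +350% | -77.8% | 12 g | 54 g | 140 g |
| Protein | 15 g | 40 g | 2.67 | +167% | -62.5% | 4.5 g | 12 g | 25 g |

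**Pairs of meals.** Eight meals give 8 × 7 / 2 = 28 pairs. Each nutrient has four meals at each level. So 2 × (4 × 3 / 2) = 12 pairs are equal, and 4 × 4 = 16 differ by the full gap. Pairs with a non-zero contrast below 62.5%: 0 of 28 for carbohydrate and 0 of 28 for protein.

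**Can the shape be checked?** A model with intercept, carbohydrate, protein, fat, carbohydrate² and protein² has six columns. On the eight meals its design matrix has rank 4. Curvature in carbohydrate and protein is not estimable, and more participants do not change this.

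**What the shape does to intermediate intakes (illustration).** Take two curves that pass exactly through both fed levels L and H, and let f be the fraction of the low-to-high response. The intake read off is L + (H − L)f if linear and L × (H/L)^f if log-linear.

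- Carbohydrate, f = 0.5: 110 g against √(40 × 180) = 84.9 g; 110 / 84.85 = 1.296. The largest ratio is 1.316, at f = 0.379 (93.1 against 70.7 g).
- Protein, f = 0.5: 27.5 g against √(15 × 40) = 24.5 g; 27.5 / 24.49 = 1.123. The largest ratio is 1.126, at f = 0.420 (25.5 against 22.6 g).

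**What the shape does to power for a 30% step (illustration).** The step's share of the fed contrast is:

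- Carbohydrate, 40 to 52 g: 12/140 = 8.6% if linear; ln 1.3 / ln 4.5 = 17.4% if log-linear.
- Protein, 15 to 19.5 g: 4.5/25 = 18.0% if linear; ln 1.3 / ln 2.667 = 26.7% if log-linear.

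If residual variance is constant (my assumption), the n needed scales with the inverse square of the share. The two shapes then differ by (17.4/8.6)² ≈ 4.1 for carbohydrate and (26.7/18.0)² ≈ 2.2 for protein. Both curves fit the two fed levels equally well, so the study's data cannot choose between them.

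**The case against.** The best defence is that nothing here is contradictory. Section 7.0 names a difference that a model should resolve; it does not promise to feed that difference. In calibration, resolution follows from slope and residual error, and widely spaced levels estimate a slope well. This stands: sizing for a smaller difference than the one fed is not an error in itself. But the argument needs a known shape between the levels, and this design cannot supply evidence for one.

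A second defence is that functional form belongs in the analysis plan, which is not at hand. That is fair for the choice of model. But the sizing target and the meals are both fixed in the Protocol, and no analysis plan can create an intermediate level. Nor do repeated samples or several analytes help, since every feature of the response is still seen at only two intakes. The pre-meal sample lies outside both fed ranges, and no zero-gram meal is fed and followed.

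A third defence is that the illustration is selective. This largely stands. The gap of about 30% comes from two chosen curves and holds only for carbohydrate, where the Protocol regards glucose behaviour as well studied. For protein, whose link to ISF amino acids it calls less understood, the gap is at most 12.6%. An interpolation gap is also not the same quantity as a detectable difference.

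Finally, the primary endpoint concerns the set meals, and the prediction of amounts appears in the background text. This also stands, and it supports limiting the conclusions to the fed levels.

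**Conclusion.** The point holds as a fault in the power statement of Section 7.0, not in the design. The 30% resolution is not observable in this study: 0 of 28 meal pairs has a non-zero contrast below 62.5% for either nutrient. It could be claimed only by interpolating under a shape that two levels cannot test. That conclusion needs only Table 1 and the wording of Section 7.0. The figures for intermediate intakes and for relative sample size are illustrations that depend on the linear and log-linear curves and, for the latter, on constant residual variance.

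Three stronger readings are tempting and not supported:

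- A reader might infer that 33 is too few. The Protocol gives no variance, so this cannot be judged.
- A reader might infer that the study cannot separate its meals. The fed contrasts are large (4.5-fold and 2.67-fold), and nothing suggests that they are underpowered.
- A reader might infer that the sponsor intends to present separation of the fed levels as proof of 30% resolution. No section says so; the present wording merely leaves it open.

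**What to change.** In Section 7.0, state power for the contrasts actually fed (carbohydrate 40 against 180 g, protein 15 against 40 g), using the sponsor's own variance inputs. Give the rationale for 33 separately, for example the data needed to train the model. Add that conclusions are limited to the fed levels, that separating those levels does not demonstrate 30% resolution, and that any prediction at an intermediate intake depends on an assumed intake-response shape.

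The cost is a less ambitious stated claim, variance inputs that the Protocol does not now show, and a short new justification for 33. Participants, meals and procedures do not change.

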 - The investigator is responsible for determining the actions that need to be taken to ensure participant safety. The investigator will submit any unapproved actions to the IRB and these actions may not be initiated without IRB review and approval except when necessary to eliminate apparent immediate hazards to the participant. The IRB may identify additional measures that need to be taken.
 - In case a protocol deviation happens which is a failure to follow the protocol due to the action or inaction of the investigator or research staff will be reported within 5 business days.

15.0 Withdrawal of Participants:

Participants are informed and reminded during all research activities that they are able to discontinue or omit procedures at any point without reason.

IRB NUMBER: IRB2023-0400F
IRB APPROVAL DATE: 4/10/2024

Participants who are unwilling or unable to complete a full study day will be withdrawn from scheduling the remainder of the visits. They will be compensated for any visits completed.

All completion information including date and reason for early exit is recorded in the REDCap project.

16.0 Risks to Participants:

- Demographic and Socioeconomic Questions: Responding to demographic and socioeconomic questions could cause you to feel uncomfortable or upset. Please tell the study staff if you feel uncomfortable or upset while answering the questions.
- Pain
- Bleeding
- Mild hematoma
- Bruising
- Fluid retention (edema, increased blood pressure) associated with stable tracer ingestion or any adverse reactions during the tracer ingestion that suggest allergic reaction or infection (fatigue, body ache, nausea, vomiting, headache, urticaria, flushing, sweating, chills, altered heart rate, hypo/hypertension, and hyperthermia)
- Anemia (increased need for transfusion)
- Infection associated with peripheral catheter placement repeated blood sampling from the catheter
- Vaso-vagal response associated with peripheral catheter placement
- Skin rash associated with an allergic reaction to tape or other medical disposables used for study purpose
- While using the temperature controlled box, in people with poor circulation or frail skin, scalding may occur after prolonged exposures in the temperature controlled box.
- Gastrointestinal problems like nausea, bloating, diarrhea and vomiting associated with the intake of the test meal(s)

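### At the stated 20% dropout, the ceiling of 40 enrolled leaves 32 expected completers, one fewer than the 33 that section 7.0 says are needed

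*Protocol*

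**What the plan says.** Section 7.0 (Number of Local Participants) holds the protocol's only sample size statement, and all three figures stand in one paragraph.

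- Ceiling: "Up to 40 individuals will be enrolled in the study".
- Number needed and expected loss: "we will need 33 healthy participants, 8 meals per participant. Estimating 20% dropout".
- Basis for the 33: a calculation for the machine-learning model to "distinguish a 30% difference in protein and CHO amounts", "with power of 0.8 and significance level of 0.05".

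The paragraph gives no variance, test, within-person correlation or sidedness, and does not show how 40 was obtained. Section 11.0 provides two meals on each of four study days. Section 15.0 adds: "Participants who are unwilling or unable to complete a full study day will be withdrawn from scheduling the remainder of the visits". No section provides for replacing dropouts or for enrolling more than 40.

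**The concern.** The ceiling, the number needed and the dropout rate are linked by simple arithmetic: any two determine the third. Here they do not fit. If 33 is the number of participants who must supply all eight meals, a cap of 40 with 20% lost does not deliver it in expectation.

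What is at stake is small. The plan expects to finish just under its own stated size, so the target power of 0.8 is not quite supported by its own cap and dropout figure. The text asks for 33 while its other two figures lead to 32, and it does not say which is to be taken as the planned number of completers.

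**Working it through.** **Inputs (protocol section 7.0):** enrolment ceiling 40; number needed 33, with 8 meals each; dropout 20%; power 0.8; significance level 0.05.

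**1. Reproducing the 40.** The 33 itself cannot be reproduced, because its inputs are not given. The 40 can be matched by adding 20% to the number needed:
33 × (1 + 0.20) = 39.6, rounded up to 40.
This is consistent with the stated cap but does not prove how the cap was set.

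**2. Expected completers under the cap.**
40 × (1 − 0.20) = 32. Shortfall: 33 − 32 = 1.
In participant-meals from completers: 33 × 8 = 264 needed, 32 × 8 = 256 expected.

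**3. Enrolment needed to keep 33 at 20% dropout.**
33 / (1 − 0.20) = 41.25, rounded up to 42.
Check: 41 × 0.8 = 32.8 (short); 42 × 0.8 = 33.6 (enough).

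**4. Dropout that the cap can absorb.**
(40 − 33)/40 = 7/40 = 17.5%.

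**5. Chance of reaching 33.** Assuming participants drop out independently, each with probability 0.2:

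| Enrolled | P(at least 33 complete) |
|---|---|
| 40 | 0.437 |
| 41 | 0.562 |
| 42 | 0.676 |

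**6. Power at 32.** Assumptions: 33 gives exactly 0.80; two-sided 0.05; normal approximation with the noncentrality proportional to √n.
Φ((1.960 + 0.8416) × √(32/33) − 1.960) = 0.788.
With a one-sided 0.05 test the result is 0.789. If 33 was rounded up from a fraction, power at 32 is higher. At the other limit, where 32 only just misses 0.80, power at 33 is about 0.812. So two-sided power at 32 lies between 0.788 and just under 0.80.

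**The case against.** The case for leaving this alone has four parts.

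*It is immaterial.* One participant and about 1.2 points of power lie within ordinary planning tolerance, and the 20% is only an estimate. This stands as a comment on size. It does not make the three figures agree.

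*The figures fit on another reading.* If the 20% is an allowance on top of the 33, then 33 × 1.2 = 39.6 gives 40. But dropout acts on those enrolled, and 20% of 40 leaves 32; adding the percentage to the number needed is the usual inflation mistake. A third reading is that 33 already includes dropout (26/0.8 = 32.5, rounded up to 33). That leaves the 40 without a basis, and 26 appears nowhere in the protocol.

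*Partial data could fill the gap.* Each study day yields two meals, so four of the eight expected dropouts completing one day each would supply the 8 missing participant-meals. Section 15.0 stops later visits but does not say that data already collected are discarded. This is possible but not established: the protocol does not say that incomplete participants are analysed, and it states its need as 33 participants with 8 meals each.

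*The power figure rests on an outside model.* This is correct. The calculation was for a machine-learning model whose inputs are not given, so 0.788 indicates the order of the loss and is not a property of this plan. Likewise, the 44% chance of reaching 33 should be set against the 68% from 42 enrolled: even correct inflation would miss 33 about a third of the time.

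**Conclusion.** The inconsistency is real and minor. With the protocol's own cap and dropout rate, 32 completers are expected against 33 needed. The arithmetic rests only on section 7.0, given that 33 means participants who complete all eight meals. That is the natural reading, since the number is the output of the sample size calculation and is tied to eight meals each, but the text does not spell it out. The power cost, under the assumptions in the working, is at most about 1.2 percentage points. That is no threat to the study; the reason to act is that the sole sample size statement does not agree with itself.

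**What to change.** Rewrite one sentence in section 7.0 so that the figures agree, keeping 40 enrolled. There are two ways.

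1. **Preferred.** State 40 enrolled, 20% dropout and 32 expected completers, with power slightly below 0.8. The sponsor recomputes the power from its own sample size inputs.
2. **Alternative.** State 40 enrolled, with 33 retained provided dropout is at most 17.5% (7 of 40). This describes correctly what the cap allows, but it assumes less dropout than the 20% now stated, and the protocol gives no evidence for the lower rate.

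The same sentence should say that the number refers to participants who complete all eight meals. Either version costs one sentence and leaves enrolment unchanged; the first openly accepts a power just under 0.8. Raising the cap to 42 would also reconcile the figures, but two more participants are hard to justify for a difference of this size.

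### Each test meal is fixed to the morning or the afternoon slot and only the order of meal sets is randomised, so macronutrient content is confounded with first versus second meal of the day

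*Protocol*

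**What the plan says.** Section 11.0 of the protocol describes up to eight meals, "with specific nutritional composition (two per day) and then monitored for four hours after the meal". On timing it adds: "Meals will be spaced at 8 hours to limit overlapping effects".

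Table 1 defines the meals by two levels each of carbohydrate (40 or 180 g), protein (15 or 40 g) and fat (15 or 40 g). All eight combinations appear, so the meals form a full 2×2×2 factorial.

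Table 2 pairs the meals into four sets under fixed morning and afternoon columns, for example "Meal set A Meal 1 Meal 4 1595", "Meal set B Meal 6 Meal 7 1595" and "Meal set C Meal 2 Meal 3 1595". Set D has meal 5 in the morning and meal 8 in the afternoon.

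On randomisation, the sentence under Table 2 reads: "Meal sets will be randomized across study days for all participants". The text before Table 1 says the same. The table caption is looser, "Table 2. Meal sets to be randomized across the study day", but the columns below it are labelled by time of day. Nothing in the protocol says that the order of the two meals within a set is randomised, swapped or balanced.

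**The concern.** The objective (Section 4.0) is a quantitative relation between macronutrient intake and metabolite levels in blood and interstitial fluid. The primary endpoint (Section 10.0) is a set of prediction models tied to the macronutrient content of the meals. Both need the meal effect to be separable from other causes of a changed response.

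The second meal of the day differs from the first in several ways: it comes 8 hours after another test meal, after more hours with the catheters in place, and at another time of day. If those differences alter the metabolite response, and richer meals are mostly given second, a model will credit the difference to the macronutrients. A flexible model may also appear to recognise the meal when it is partly recognising the slot.

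There is a second layer. Each afternoon meal always follows the same morning meal, its exact complement. Any signal left over from the morning is therefore also tied to the composition of the afternoon meal.

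**Working it through.** **Inputs.** Meal compositions and energies come from Table 1, and slots from Table 2. The sample size is 33 participants with 8 meals each, with power 0.8 and significance level 0.05 (Section 7.0).

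**Check that the tables are read correctly.** Energy = 4 × carbohydrate + 4 × protein + 9 × fat reproduces all eight energies in Table 1. Morning plus afternoon energy is 1595 kcal for every set (A: 355 + 1240; B: 455 + 1140; C: 580 + 1015; D: 915 + 680), as Table 2 states.

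**Step 1: code the factors.** High = +1, low = −1; afternoon = +1, morning = −1.

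| Meal | C | P | F | C·P·F | (C+P+F−CPF)/2 | Slot in Table 2 |
|---|---|---|---|---|---|---|
| 1 | −1 | −1 | −1 | −1 | −1 | morning |
| 2 | −1 | −1 | +1 | +1 | −1 | morning |
| 5 | +1 | −1 | −1 | +1 | −1 | morning |
| 6 | −1 | +1 | −1 | +1 | −1 | morning |
| 3 | +1 | +1 | −1 | −1 | +1 | afternoon |
| 4 | +1 | +1 | +1 | +1 | +1 | afternoon |
| 7 | +1 | −1 | +1 | −1 | +1 | afternoon |
| 8 | −1 | +1 | +1 | −1 | +1 | afternoon |

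Slot = (C + P + F − CPF)/2 holds for all eight meals. Morning meals have at most one high macronutrient; afternoon meals have two or three.

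**Step 2: imbalance.** Means, morning versus afternoon:
- carbohydrate: 75 vs 145 g
- protein: 21.25 vs 33.75 g
- fat: 21.25 vs 33.75 g
- energy: 576 vs 1019 kcal

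The correlation of slot with each macronutrient is 0.50. Guessing high in the afternoon and low in the morning is right for 3 of 4 meals in each slot, so slot alone classifies each macronutrient with 75% accuracy (chance 50%).

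**Step 3: slot left out of the model.** Of the meals high in a given macronutrient, 3/4 are afternoon meals; of those low in it, 1/4 are. The high-minus-low contrast therefore carries (3/4 − 1/4) = 0.5 times the afternoon-minus-morning difference as bias.

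The protocol gives no size for that difference. As an illustration, assume a within-person SD of 0.3, a true protein effect of 0 and 33 × 8 = 264 meals. Simulation (600 trials per scenario, standard error 0.037) gives:

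| Assumed slot effect | Spurious protein effect | Called significant |
|---|---|---|
| 0.1 | 0.05 | about 26% |
| 0.2 | 0.10 | about 77% |
| 0.3 | 0.15 | about 98% |

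**Step 4: slot put in the model.** With main effects and slot, the model has full rank (5 of 5). For one macronutrient, given the other two and slot, R² = 0.5²/(1 − 0.5² − 0.5²) = 0.5, so the variance inflation factor is 1/(1 − 0.5) = 2.0. It is also 2.0 with set (day) effects in the model. The standard error rises by √2 − 1 = 41%.

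For a contrast planned at 80% power, power becomes Φ((1.960 + 0.842)/√2 − 1.960) = Φ(0.021) ≈ 0.51. Restoring 80% needs 33 × 2 = 66 participants, assuming the 33 was computed without a slot term.

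**Step 5: interactions.** With all interactions plus slot, the design has rank 8 for 9 columns. Slot can then be separated from the meals only by assuming that the three-way interaction is zero.

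**Step 6: order counterbalanced within sets.** The correlation of slot with each macronutrient becomes 0 and every variance inflation factor becomes 1.0. In the same simulation the standard error with slot in the model is 0.037, against 0.052 under the fixed order.

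**The case against.** The facts of Table 2 and the arithmetic are hard to dispute. The case on the other side concerns degree and remedy.

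- **The confounding with any one macronutrient is partial.** This stands. At r = 0.50 an additive model with a slot term still estimates the main effects. Confounding is complete only for the individual meal and for models with the three-way interaction.
- **The harm depends on an unknown slot effect.** This also stands. The protocol supports only a bias of half an unstated difference; the false-positive rates above are illustrations. The macronutrient contrasts are large by design, and a small slot effect might matter little beside them.
- **The 51% is not this trial's power.** Correct. Section 7.0 gives no test, SD or covariates for its machine-learning calculation. The figure shows what doubling the variance does to a main-effect contrast.
- **The listed model inputs are metabolites, not clock time.** True, and high/low classification is not a stated endpoint. The 75% is a benchmark; a model exploits slot only if the metabolites reveal it.
- **There is a baseline sample before each meal, and the meals are 8 hours apart.** Baselines remove additive offsets, and spacing limits carry-over. Neither corrects a changed response to a second meal.
- **A slot term may be in the analysis plan.** It may, but the defect lies in the allocation. No analysis can separate slot from meal identity without the assumption in Step 5.
- **Swapping the order leaves each meal paired with its complement.** True. The swap does supply observations of every meal as the first of the day, but it does not break the pairing.

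**Conclusion.** The concern holds and should be fixed before further meals are given. As written, every meal is tied to one slot, and all three macronutrients are unbalanced over slot in the same direction (r = 0.50 each). Leaving slot out biases each main effect by half the slot difference. Putting it in doubles the variance and requires a zero three-way interaction. Randomising sets over days gives no protection, because slot varies within the day.

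These results follow from Tables 1 and 2 alone. The size of the actual bias does not, because the slot effect is not given. The 51% power and the 66 participants rest on the assumption that the planned 33 ignored slot. Figure 1, the study-day overview, was not available to check; the text and both tables show no counterbalancing.

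**What to change.** Keep the four sets and the 1595 kcal daily total. Randomise which meal of each set comes first, balanced over participants so that each meal appears equally often, or as nearly as numbers allow, in both slots. Reword Table 2 and the randomisation sentence to match, and include slot as a term in the models.

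If the fixed order must stay, put slot in every model, state that the main effects rest on a zero three-way interaction, report high/low accuracy against the 75% slot-only benchmark, and restate the power. This is second best, because it cannot recover the lost information.

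The cost is a protocol amendment and a new randomisation list, with no extra visits, meals, samples or participants. There is one trade-off. Mean morning energy would rise from 576 to 1595/2 = 797.5 kcal, and meals 3, 4 and 7 (1015 to 1240 kcal) would come first in half of their exposures, leaving more to clear before the second meal. Meal 5 (915 kcal) is already a morning meal with the same 8-hour gap. Data already collected in the fixed order would keep the aliasing.
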